#### **10.3.2. Procedures for Early Withdrawal**

If a patient withdraws or is removed from the study for any reason, all early withdrawal procedures should be completed. Reason for withdrawal, date of the discontinuation, and date of the last dose of study drug should be recorded in the appropriate section of the eCRF. Additionally, the discontinuation visit date must be registered in IWRS. Study drug assigned to the withdrawn patient may not be assigned to another patient.

All effort should be made to have each patient complete all study visits on schedule according to the protocol. Accommodations for early or late visits in special circumstances will be considered by the Sponsor to prevent early withdrawal. Written notice (regardless of cause) is to be provided within 48 hours of the withdrawal to the Sponsor personnel or the Medical Monitor. At the time of discontinuation, every effort should be made to ensure all relevant procedures and evaluations scheduled for the final study visit are performed. Except in the case of a medical emergency, the procedures and assessments detailed in [Section 10.2.8](#) will be performed upon the discontinuation of the study.

Patients choosing to withdraw from the study early should be encouraged to return for all study scheduled clinic visit even if they are no longer taking IMP. Patients who withdraw from all aspects of the study will be asked to consent to clinical visits or phone calls for safety assessments, *including AEs, concomitant medication, and current health status* through Week 52 (Visit T7)

## **11. ASSESSMENT OF SAFETY**

### **11.1. Safety Parameters**

At all clinic visits, investigators will review all safety information including vital signs, AEs, concomitant medications, and ECG reports and will ensure that the collected data are recorded into the appropriate eCRF. Additionally, clinical laboratory samples will be collected and sent for analysis and the investigator will review the results to ensure continued patient safety while participating in the study.

#### **11.1.1. Demographic/Medical History**

Demographic data and a complete medical history will be obtained from the patient. For medical history, conditions that are relevant and/or clinically significant should be captured with at least a start date (month and year) and whether the condition is ongoing or resolved. All surgeries regardless of date should be reported.

#### **11.1.2. Vital Signs**

Vital signs will include diastolic and systolic blood pressure as well as heart rate.

The patient should sit quietly for 5 minutes prior to collection of vital signs. At all time points, vitals will be collected prior to blood collection. Blood pressure and heart rate will be measured using a calibrated, fully automated machine with a cuff that is appropriate to the size of the upper arm. If a fully automated machine is not available, blood pressure may be measured manually. The same method (either automated or manual) and the same arm (right or left) must be used throughout the study. The patient should be in a seated position with feet touching the floor. Patients should be seated quietly for at least 5 minutes in a chair with their backs supported, their feet flat on the ground, and their arms bared and supported at heart level.

#### **11.1.3. Weight, Height, and Body Mass Index**

Weight will be measured on a calibrated scale in the morning while fasted and after voiding. Body weight will be measured in the morning while fasting, using consistent scales, after voiding, and without shoes and outerwear (eg, coats).

Height will be measured using standard clinic procedures.

BMI will be calculated using the formula:

$$\text{BMI (kg/m}^2\text{)} = \text{weight in kg} / (\text{height in meters})^2$$

#### **11.1.4. Physical Examination**

PEs will include an assessment of the following:

- General appearance
- Skin

- Eyes, ears, nose, and throat
- Head and neck
- Extremities
- Musculoskeletal examination
- Respiratory examination
- Cardiovascular assessment, including rhythm and presence of cardiac abnormalities
- Abdominal examination
- Neurologic examination including documentation of the presence of abnormalities in mental status and motor and sensory function
- Any additional assessments necessary to establish baseline status or evaluate symptoms or adverse experiences

Documentation of the PE findings will be included in the source documentation at the clinical site. Significant findings prior to the start of study drug will be recorded on the Medical History/Current Medical Conditions page of the eCRF. Only changes from baseline physical examination findings that meet the definition of an AE will be recorded on the AE page of the eCRF.

Note: Additional information will be collected regarding muscle-related AEs. See [Section 11.2.3](#).

### **11.1.5.    *Electrocardiogram***

ECG collection will be preceded by a 10-minute rest time during which the patient will remain in the supine position. At all time points, ECGs will be collected prior to blood collection. ECGs will be assessed using machine readings and physician review.

#### **11.1.5.1.    *Monitoring and Management of Abnormal Electrocardiograms***

If a clinically significant ECG abnormality not present at baseline (screening) is determined by the Investigator to be related to study drug, the abnormality will be discussed with the Sponsor personnel or the authorized Medical Monitor, and followed and evaluated with additional tests (if necessary) until the underlying cause is determined or the event is brought to an acceptable resolution. Additional clinical and laboratory information will be collected and carefully documented in order to better characterize the ECG abnormality and rule out alternative causes. ECG findings determined to be a clinically significant change from baseline should be reported as an AE regardless of causality.

Unscheduled ECG assessments will be completed at the discretion of the Investigator.

### **11.1.6.    *Clinical Laboratory Tests***

#### **11.1.6.1.    *Laboratory Parameters (Safety)***

Patients will be in a seated position during the blood collection. Clinical laboratory parameters and tests will include those listed in [Table 5](#). Collection schedule, schedule of laboratory

parameters by visit, and instructions are in the Clinical Laboratory Manual provided by Central Laboratory.

**Table 5: Clinical Laboratory Parameters (Safety)**

Clinical Laboratory Test	Clinical Laboratory Test

 
• Hematology
 
• Hematocrit (Hct)
 
• Hemoglobin (Hgb)
 
• Mean corpuscular hemoglobin (MCH)
 
• Mean corpuscular hemoglobin concentration (MCHC)
 
• Mean corpuscular volume (MCV)
 
• Platelet count
 
• Red blood (RBC) cell count
 
• White blood (WBC) cell count with differential (absolute and %)
 
	Blood Chemistry (serum, fasting) 
 
• Albumin (Alb)
 
• Alkaline phosphatase (Alk-P)
 
• Alanine aminotransferase (ALT; SGPT)
 
• Aspartate aminotransferase (AST; SGOT)
 
• Blood urea nitrogen (BUN)
 
• Calcium (Ca)
 
• Carbon dioxide (CO2)
 
• Chloride (Cl)
 
• Creatinine
 
• Creatine kinase (CK)
 
• Glucose
 
• Lactate dehydrogenase (LDH)
 
• Phosphorus
 
• Potassium (K)
 
• Sodium (Na)
 
• Total and direct bilirubin (TB)a
 
• Total protein
 
• Uric acid
 

Urinalysis (Dipstick) 
 
• Clarity
 
• Bilirubin
 
• Color
 
• Glucose
 
• Ketones
 
• Leukocyte esterase
 
• Nitrate
 
• Occult blood
 
• pH
 
• Protein
 
• Specific gravity
 
• Urobilinogen
 
	

**Table 5: Clinical Laboratory Parameters (Safety) (Continued)**

Clinical Laboratory Test	Clinical Laboratory Test
Urinalysis (Microscopic)-only if urine dipstick abnormal 
 
• Bacteria
 
• Casts
 
• Crystals
 
• Epithelial cells
 
• Red blood cell (RBC)
 
• WBC
 
	Coagulation—In all patients at screening, then only in patients receiving anticoagulant therapy that in the investigator's judgment require monitoring at Visit T1 and 3 to 5 days post Visit T1 
 
• Prothrombin time (PT)
 
• International normalized ration (INR)
 

Other Screening Labs 
 
• Hepatitis B surface antigen (HBsAg), hepatitis C virus (HCV)b
 
• Serum pregnancy test (only for females of childbearing potential)
 
• Follicle-stimulating hormone (FSH; Females <55 years and >1 year without menses)
 
• Urine pregnancy test prior to randomization (for females of childbearing potential)
 
• Thyroid-stimulating hormone (TSH)
 
	Additional samples 
 
• Hemoglobin A1C (HbA1C)
 
• Reserve blood samples for potential future measurement of ETC-1002 safety or pharmacodynamic biomarkers
 
• PK sample (patients randomized after Protocol Amendment 3 and subsequent amendments are excluded from PK sampling)
 
• Reserve genetic blood sample (optional)
 

a If  $TB \geq 1.2 \times ULN$ , a reflex indirect (unconjugated) bilirubin will be obtained.

b If HCV-AB is positive, a reflex HCV RNA will be performed to rule out active disease.

### 11.1.6.2. Sample Collection, Storage, and Shipping

Clinical laboratory samples will be collected by appropriate clinical site personnel and then shipped according to a separate laboratory manual provided by the Central Laboratory. For collection and processing of PK samples, please see [Section 11.1.6.4](#) and [Section 11.1.6.6](#).

Samples will be processed by the Central Laboratory, and PK samples will be forwarded to the Bioanalytical Laboratory for analysis. Reserve samples will be stored frozen for potential future measurement of additional ETC-1002 safety and efficacy biomarkers. A reserve genetic blood sample (optional) will also be stored frozen for potential future ETC-1002 genetic analyses.

Blood draws for lipids, TG, and glucose must meet the criteria listed below. If these criteria have not been met, these blood samples will NOT be collected. If these criteria can be met by rescheduling the clinic visit to occur within 3 days, the lipid, TG, and/or glucose blood samples will be collected at the rescheduled clinic visit only.

- Blood samples will be drawn after a minimum 10-hour fast (water is allowed)

### **11.1.6.3. General Monitoring and Management of Abnormal Clinical Labs**

It is the Investigator's responsibility to review the results of all laboratory tests as they become available and to sign and date the *report to document their* review. For each laboratory test outside of the laboratory normal range, the Investigator needs to ascertain if this is a clinically significant change from baseline for the individual patient, with baseline defined as the last value or observation before the first dose of study drug. The Investigator may repeat the laboratory test or request additional tests to verify the results of the original laboratory test.

If a laboratory value is determined to be an abnormal and clinically significant change from baseline for the patient, the Investigator should determine if it qualifies as an AE, and if yes, an appropriate eCRF will be completed. All clinically significant laboratory abnormalities occurring during the study that were not present at baseline should be followed and evaluated with additional tests if necessary, until diagnosis of the underlying cause or resolution. Specific monitoring and management guidelines for laboratories of special interest are outlined in the sections below.

#### **11.1.6.3.1. Monitoring and Management of Elevated Liver Function Tests**

If at any time after randomization a patient experiences a new ALT and/or AST  $>3 \times$  ULN, the patient will undergo repeat confirmatory LFT assessment as soon as is reasonably possible, preferably within 3 to 7 days of the laboratory result becoming available.

Repeat LFT assessment will include: 1) measurement of ALT, AST, alkaline phosphatase, total and direct bilirubin, prothrombin time (PT)/international normalized ratio (INR), eosinophil count, CK, antihepatitis A virus (total), HBsAg (confirmation of screening measurement), HCV (confirmation of screening measurement), and anti-cytomegalovirus/immunoglobulin M; 2) history of concomitant medication use; 3) history of exposure to environmental chemical agents, including ethanol; and 4) query for related symptoms. Additionally, further testing such as liver ultrasound or MRI scanning may be warranted to rule out additional pathology depending on clinical presentation and should be discussed with the Sponsor personnel or the authorized Medical Monitor.

- If repeat LFT assessment confirms ALT and/or AST  $>3 \times$  ULN, consideration should be given to withdrawing the patient and administering no further doses of study drug. At the investigator's discretion, study drug may be interrupted and the patient rechallenged with study drug after LFTs have returned to baseline levels.
- If repeat LFT assessment confirms ALT and/or AST  $>5 \times$  ULN, patient should be withdrawn from IMP treatment, but will be asked to continue to be followed for safety using the protocol-specified visit schedule (see [Appendix 1](#)).

- If repeat LFT assessment confirms ALT and/or AST  $>3 \times$  ULN in addition to any of the following, the patient should be given no further IMP treatment, but will be asked to continue to be followed for safety using the protocol-specified visit schedule (see [Appendix 1](#)):
  - TB  $>2 \times$  ULN  
*Note: In the case of patients with Gilbert's disease, TB will be fractionated and the determination of  $2 \times$  ULN will be based upon direct (conjugated) bilirubin.*
  - INR  $>1.5 \times$  ULN (unless the patient is on stable dose of anticoagulation medication)
  - Appearance or worsening of right upper abdominal discomfort, anorexia, fatigue, nausea, vomiting, fever, rash, or eosinophilia

#### **11.1.6.3.2. Monitoring and Management of Elevated Serum Creatinine**

If at any time after randomization, a patient experiences a decrease in eGFR to the level of 15 mL/min/1.73 m^2) or if the patient experiences acute renal failure, the patient should be withdrawn from IMP treatment but will be asked to continue to be followed for safety using the protocol-specified visit schedule (see [Appendix 1](#))

#### **11.1.6.3.3. Monitoring and Management of Hemoglobin Change**

If at any time after randomization a patient experiences a decrease  $>2.0$  g/dL (20 g/L) from baseline (Week 0 [Visit T1]), the patient will undergo repeat confirmatory hematology testing as soon as is reasonably possible, preferably within 3 to 7 days of the laboratory result becoming available.

Repeat hematology assessment will include: 1) measurement of Hgb, hematocrit (Hct), mean corpuscular hemoglobin, mean corpuscular hemoglobin concentration, mean corpuscular volume, platelet count, reticulocyte count (percent and absolute), red blood cell count (RBC), and white blood cell count (WBC) with differential (absolute values only); 2) history of concomitant medication use; and 3) query for related symptoms. Additionally, further testing may be warranted to rule out additional pathology depending on clinical presentation, and should be discussed with Esperion Therapeutics personnel or the authorized [REDACTED] Medical Monitor.

- If repeat Hgb assessment confirms a decrease  $>2.0$  g/dL (20 g/L) from baseline, the patient should be monitored carefully during the study and return at 2 week intervals after study completion for additional Hgb measurement until the level returns to baseline or reaches a stable level.
- If repeat Hgb assessment confirms Hgb  $<8$  g/dL (80 g/L), the patient should be withdrawn from IMP treatment. The patient will return at 1-week intervals after withdrawing from IMP treatment for additional Hgb measurement until the level returns to baseline or reaches a satisfactory conclusion.
- If the patient is withdrawn from IMP treatment, the patient should be asked to continue being followed for safety using the protocol-specified visit schedule (see [Appendix 1](#)).

At any time, the investigator may choose to consult with a specialist to further evaluate the cause of the alteration in hemoglobin.

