7. Uncontrolled hypertension, defined as sitting systolic blood pressure (SBP)  $\geq 160 \text{ mmHg}$  and diastolic blood pressure (DBP)  $\geq 100 \text{ mmHg}$  after sitting quietly for 5 minutes. Note: If the initial blood pressure (BP) values meet or exceed the specified level, an additional BP assessment may be completed. If the systolic or the diastolic values continue to meet or exceed the threshold, the patient may not continue screening. However, at the discretion of the Investigator, the screening period may be extended up to 2 weeks to allow for a repeat qualifying BP assessment following adjustment of BP medication(s), provided that the patient has been on a stable dose of the BP medication for a minimum of 2 weeks prior to randomization and the repeat BP measurements do not meet the exclusion criteria
8. Hemoglobin A1C (HbA1C)  $\geq 10\%$  at Week -2 (Visit S1)
9. Uncontrolled hypothyroidism, including thyroid-stimulating hormone (TSH)  $>1.5 \times$  the upper limit of normal (ULN) at Week -2 (Visit S1). Patients stabilized on thyroid replacement therapy for at least 6 weeks prior to randomization are allowed.

10. Liver disease or dysfunction, including:

- Positive serology for hepatitis B surface antigen (HBsAg) and/or hepatitis C antibodies (HCV-AB) at Week -2 (Visit S1); or
- Alanine aminotransferase (ALT), aspartate aminotransferase (AST)  $\geq 2 \times$  ULN, and/or total bilirubin (TB)  $\geq 1.2 \times$  ULN at Week -2 (Visit S1).

*Note: If HCV-AB is positive, a reflex HCV RNA will be performed to rule out active disease. Patients without active disease may be enrolled in the study.*

Note: At the discretion of the investigator, the screening period may be extended up to 2 weeks for a single repeat of ALT, AST, and/or TB. For those patients who have a repeat ALT, AST, and/or TB, the repeat value will be used to determine eligibility.

*If TB  $\geq 1.2 \times$  ULN, a reflex indirect (unconjugated) bilirubin will be obtained and if consistent with Gilbert's disease, the patient may be enrolled in the study.*

11. Gastrointestinal conditions or procedures (including weight loss surgery; eg, Lap-Band® or gastric bypass) that may affect drug absorption
12. Hematologic or coagulation disorders or a hemoglobin (Hgb) level  $< 10.0$  g/dL (100 g/L) at Week -2 (Visit S1)

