#### 10.2.1. Screening Week -2 (Visit S1; Days -16 to -4)

The screening period will begin with a screening visit that will occur 2 weeks prior to randomization. Visit S1 will allow the Investigator to assess the patient's preliminary eligibility. After the patient provides written informed consent (see Section 10.1), the patient will undergo the following assessments and procedures at Visit S1:

- Demographics
- Clinically relevant medical history, including assessment of HeFH status and ASCVD
- Concomitant and prohibited medication review
- Height (cm), weight (kg), BMI
- Vital signs
- Clinical laboratory evaluations:
  - Hematology, blood chemistry, coagulation, and urinalysis
  - Basic fasting lipids (TC, calculated LDL-C, HDL-C, non-HDL-C, and TG)
  - HbA1C
  - TSH
  - *FSH (in appropriate female patients)*
  - Serum pregnancy test (on appropriate female patients)

- Serology (including HBsAg, HCV)
- Review of all inclusion/exclusion criteria that can be assessed at this time
- Conduct diet and exercise counseling
- Contact IWRS to register the patient

Patients who meet all enrollment criteria that can be assessed at Visit S1 will be instructed to continue their therapy(s) for lipid regulation and to maintain consistent diet and exercise patterns throughout the study. Patients who fail to meet any entry criterion that can be assessed at Visit S1 are considered to be screen failures and are not required to return for additional visits (although a patient can be seen at any time for safety reasons).

Note:

- An optional visit approximately 1 week later MAY be completed if patient fails to meet a lipid entry criterion. If this optional visit is completed, the mean of lipid values from both visits will be used to determine eligibility.
- *An optional visit between Visits S1 and T1 may be scheduled to collect screening fasting labs in the event that the patient arrives at Visit S1 in a nonfasted state.*
- An optional visit between Visits S1 and T1 may be completed if the patient's DBP and/or SBP meet the exclusion criteria levels. Patients may randomize after blood pressure medications have been adjusted, they have been on stable doses of blood pressure medications for at least 2 weeks, and the repeat blood pressure values (DBP and/or SBP) no longer meet exclusionary values.

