#### **10.2.2. Treatment Week 0 (Visit T1; Day 1)**

Prior to scheduling Visit T1, review the screening clinical results to evaluate whether the patient continues to meet eligibility criteria.

- If the patient meets eligibility criteria, then schedule the Visit T1 and proceed with the Visit T1 procedures

If the patient has met all inclusion criteria and none of the exclusion criteria, the patient may be randomized into the double-blind treatment period. Patients who fail to meet any entry criterion prior to randomization are considered to be screen failures, will not be randomized into a treatment group, and are not required to return for additional visits. Patients are considered randomized once all eligibility criteria are confirmed and a randomization number is obtained by the IWRS on the day of first dose.

The patient will undergo the following assessments and procedures at (Visit T1)

- Concomitant and prohibited medication review (ongoing)
- Assess AEs (starting from signing of the informed consent document)
- Physical examination (PE)
- Weight
- 12-Lead electrocardiogram (ECG)
- Vital signs
- Clinical laboratory evaluations:
  - Hematology, blood chemistry, and urinalysis

*Note: Urine pregnancy test (for females of childbearing potential)*

- Basic fasting lipids (TC, calculated LDL-C, HDL-C, non-HDL-C, and TG)
- apoB
- HbA1C
- hs-CRP
- Reserve sample
- *Genetic sample (if the patient has consented to provide a genetic sample)*

- Review inclusion/exclusion criteria to establish patient eligibility
- Conduct diet and exercise counseling
- IWRS contact to obtain the patient randomization number and MED ID number for double-blind study drug
- Dispense IMP and provide dosing instructions
- Schedule next visit

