### **11.2.3. Reporting**

All AEs occurring during the course of the study (starting from signing informed consent to study completion) will be collected on the AE eCRF. Patients should be instructed to report any AE that they experience to the Investigator. Beginning with Visit S1 (Week -2), Investigators should make an assessment for AEs at each visit and record the event on the appropriate AE eCRF.

Wherever possible, a specific disease or syndrome rather than individual associated signs and symptoms should be identified by the Investigator and recorded on the eCRF. However, if an observed or reported sign or symptom is not considered a component of a specific disease or syndrome by the Investigator, it should be recorded as a separate AE on the eCRF. Additionally, the condition that led to a medical or surgical procedure (eg, surgery, endoscopy, tooth extraction, transfusion) should be recorded as an AE, not the procedure.

Any medical condition already present at screening or baseline should not be reported as an AE unless the medical condition or signs or symptoms present at baseline changes in severity or seriousness at any time during the study. In this case, it should be reported as an AE.

Clinically significant abnormal laboratory or other examination (eg, ECG) findings that are detected during the study or are present at baseline and significantly worsen during the study should be reported as AEs. The Investigator will exercise his or her medical and scientific judgment in deciding whether an abnormal laboratory finding or other abnormal assessment is clinically significant. Significant abnormal laboratory values occurring during the clinical study will be followed until repeat tests return to normal, stabilize, or are no longer clinically significant. Any abnormal test that is determined to be an error does not require reporting as an AE.

Each AE is to be evaluated for duration, severity, seriousness, and causal relationship to the investigational drug. For each AE, the following information will be recorded:

- Description of the event (eg, headache)
- Date of onset
- Date of resolution (or that the event is continuing)
- Action taken as a result of the event
- Seriousness of the event
- Severity of the event
- Outcome of the event
- Investigator's assessment of relationship to study drug.

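### The mandatory repeat blood count does not cover every haemoglobin value below the 8 g/dL withdrawal level when the Visit T1 value is below 10.0 g/dL

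*Protocol*

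**What the plan says.** Section 11.1.6.3.3 of the protocol has one trigger for a mandatory repeat: a haemoglobin fall of more than 2.0 g/dL from the Visit T1 value. When it fires, "the patient will undergo repeat confirmatory hematology testing as soon as is reasonably possible", preferably within 3 to 7 days. The rule for stopping study drug is tied to that second count. It begins "If repeat Hgb assessment confirms Hgb" and sets the level at below 8 g/dL, with weekly follow-up counts afterwards.

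Exclusion criterion 12 in Section 7.2 ("Hematologic or coagulation disorders or a hemoglobin (Hgb) level" below 10.0 g/dL) is assessed at Week -2. The heading of Section 10.2.1 places that visit at "Screening Week -2 (Visit S1; Days -16 to -4". Before Visit T1 is scheduled, Section 10.2.2 tells the site to "review the screening clinical results to evaluate whether the patient continues to meet eligibility criteria". The T1 haematology sample is drawn at the randomization visit itself, and no haemoglobin limit is given for it.

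For laboratory values in general, Section 11.1.6.3 says: "The Investigator may repeat the laboratory test or request additional tests to verify the results of the original laboratory test". Section 11.2.3 adds that significant abnormal values "will be followed until repeat tests return to normal, stabilize, or are no longer clinically significant", and leaves to the investigator the "judgment in deciding whether an abnormal laboratory finding or other abnormal assessment is clinically significant".

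**The concern.** The withdrawal level is absolute (8 g/dL), but it is reached through a trigger that is purely relative (a fall from T1). The two join up only if T1 haemoglobin is at least 10.0 g/dL, and the protocol does not require that at T1.

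The neighbouring rules do not have this problem. For liver enzymes (Section 11.1.6.3.1) the repeat is triggered above 3 x ULN, and each withdrawal condition needs at least that. For creatine kinase (Section 11.1.6.3.4) the repeat is triggered above 5 x ULN and mandatory withdrawal comes above 10 x ULN. The renal rule (Section 11.1.6.3.2) needs no repeat. In the liver and CK rules every value at the stopping level also sets off the repeat; for haemoglobin it may not.

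The protocol synopsis lists decreased haemoglobin among the effects already seen with the drug, as small group-mean shifts generally without symptoms. At stake is whether a patient who started low, and has dropped below the sponsor's own stopping level, is certain to get the confirmatory count that leads to stopping.

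**Working it through.** **Inputs.** Repeat trigger: fall > 2.0 g/dL from T1 (Section 11.1.6.3.3). Withdrawal level: < 8 g/dL on the repeat (same section). Entry floor: 10.0 g/dL at Week -2 only (Section 7.2, criterion 12). Visit days: Appendix 1. Assumption: results are reported in steps of 0.1 g/dL. The plan states no figure of its own to reproduce.

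**Step 1: the uncovered interval.** Let B be the T1 value and V a later value.

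- The repeat is mandatory if B - V > 2.0, that is V < B - 2.0.
- The withdrawal level is V < 8.0.
- A value is under the level without a mandatory repeat if B - 2.0 ≤ V < 8.0.
- That interval is non-empty only if B - 2.0 < 8.0, so only if B < 10.0.

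Boundary check: from 10.0 to 7.9 is a fall of 2.1, which fires. From 9.9 to 7.9 is a fall of 2.0, which does not.

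| T1 haemoglobin (g/dL) | Values below 8 that miss the trigger | Count |
|---|---|---|
| 10.0 or above | none | 0 |
| 9.9 | 7.9 | 1 |
| 9.8 | 7.8-7.9 | 2 |
| 9.5 | 7.5-7.9 | 5 |
| 9.0 | 7.0-7.9 | 10 |

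Larger falls from the same T1 values do fire the trigger (for example 9.5 to 7.4, a fall of 2.1).

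**Step 2: can T1 be below 10.0?** Week -2 falls on Day -16 to Day -4. With no Day 0, that is 16 to 4 days before Day 1, or up to 16 + 14 = 30 days if screening is extended by 2 weeks. Nothing in Section 10.2.2 stops randomization on the T1 haemoglobin.

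The documents give no haemoglobin distribution, so the number of such patients cannot be computed. As an illustration only, assume a within-person SD of 0.2 to 0.5 g/dL per measurement and no true change. The chance that T1 is below 10.0 is then Φ[(10.0 - S1)/(SD × √2)], where S1 is the screening value:

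| S1 (g/dL) | Chance T1 < 10.0 |
|---|---|
| 10.5 | about 4% to 24% |
| 11.0 | about 0% to 8% |
| 12.0 | at most 0.2% |

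Under this assumption, T1 below 10.0 is largely confined to patients who screen close to the floor. To be affected, they must also later fall below 8 g/dL by no more than 2.0.

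**Step 3: the delay if no one repeats the count.** Scheduled on-study haematology is on Days 29, 57, 85, 169, 253 and 365. The gaps are 28, 28, 84, 84 and 112 days, against the 3 to 7 days preferred in Section 11.1.6.3.3. Patients on simvastatin 40 mg have extra counts on Days 112 and 196, which split each 84-day gap into 27 and 57 days. This matters little, because the SAP's summary of changes says these patients were taken off study treatment under Amendment 5.

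**Step 4: other routes to a repeat.** The optional repeat (11.1.6.3), follow-up of significant values (11.2.3), monitoring of adverse events (11.2.6), extra safety visits (10.2) and the investigator's duty to interrupt treatment (10.3.1) could each lead to a confirming count, and so to the withdrawal rule. None of them sets a number.

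**The case against.** The strongest reply is that the thresholds fit the population admitted: 10.0 - 2.0 = 8.0, so no one at or above the entry floor at T1 is missed. The remaining patients need a narrow sequence of events. They must screen at 10.0 or more, be lower at T1, and later fall below 8 by no more than 2.0. Criterion 12 also excludes haematologic disorders, and criterion 16 excludes blood donation, transfusion, major trauma and surgery in the 30 days before randomization. The Amendment 1 log shows that an absolute repeat trigger at below 10 g/dL was removed, so a relative trigger looks deliberate.

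The existing duties are also more than permissive. Investigators must assess every out-of-range value for clinical significance and sign the report. Once a value is judged significant, Section 11.2.3 requires follow-up with repeat tests. Most investigators would act on a haemoglobin below 8 g/dL, and the data monitoring committee also reviews safety data. The Clinical Laboratory Manual, which is not among the documents, may contain alert values.

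Much of this stands, and it limits the weight of the point: the group is probably very small and a missed repeat is unlikely. It does not close the gap. Each fallback begins with a judgement that the value is significant, while the section itself sets a number. Removing a trigger at 10 g/dL also does not show an intention to leave values below the withdrawal level without a repeat.

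**Conclusion.** The concern holds. When T1 haemoglobin is below 10.0 g/dL, which the protocol allows, values from B - 2.0 to 7.9 g/dL are under the withdrawal level without making the confirmatory count mandatory. Stopping study drug then depends on investigator judgement.

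The boundary at 10.0 g/dL is exact and follows from the protocol's own thresholds; the counts of missed values assume reporting in 0.1 g/dL steps. The number of patients affected is probably very small and cannot be estimated from the documents. Whether the Clinical Laboratory Manual adds an alert value is unknown.

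No endpoint or analysis is affected: SAP Section 5.4.6 tabulates haemoglobin below 8 g/dL from all post-baseline values. That tabulation does not act on individual patients, so it does not replace the trigger. This is a safety-rule correction of low practical weight that is worth making because it is cheap.

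**What to change.** In Section 11.1.6.3.3, extend the repeat trigger to: *a decrease >2.0 g/dL (20 g/L) from baseline (Week 0 [Visit T1]) or any Hgb <8 g/dL (80 g/L)*. Leave the rest of the section as it is. The uncovered interval is then empty for every T1 value.

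The cost is one clause and a few extra blood counts within a procedure that already exists. The change does not restore the broader repeat trigger at below 10 g/dL; it adds one only at the existing withdrawal level.
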